22 performed by an expert hepatopathologist blinded to the clinical information using the modified
23 Ishak scoring system. This includes the histological activity index (HAI) for inflammation and
24 necrosis (scores ranging from 0 to 18). Fibrosis will be staged using the Ishak scoring system (0-
25 6, 0=no fibrosis, 6=cirrhosis). Slides will also be immunostained for HBsAg, HbcAg, and HDV
26 antigen by peroxidase-antiperoxidase techniques and scored as 0, 1, 2 or 3+ based upon the
27 percent of cells reactive for each viral antigen (0=none, 1=10%, 2=11% to 50% and 3= \geq 51% of
28 hepatocytes).

29 Liver-infiltrating lymphocytes will be assessed for frequency and function of NK cells. m-RNA
30 levels of ISG's, immune cell markers and chemokines/cytokines will be quantitated by real-time
31 PCR or nanostring. Intrahepatic pregenomic and cccDNA will also be quantitated by Southern
32 blotting or real-time PCR.

33
34 The following will be obtained on admission:

- 35 1) Brief clinical evaluation
- 36 2) Review patient's eligibility for study

- 1 3) Symptom questionnaire
- 2 4) Visual analogue scale
- 3 5) Fatigue questionnaire (Promise 7)
- 4 6) Abdominal ultrasound, CXR and 12 lead ECG (if not done within previous 6 months)
- 5 7) Chemistry 20 (sodium, chloride, potassium, bicarbonate, calcium, phosphate, magnesium,
- 6 glucose, blood urine nitrogen, creatinine, uric acid, ALT, AST, LDH, CPK, Alkaline
- 7 Phosphatase, total and direct bilirubin, albumin, total protein), CBC (hematocrit, hemoglobin,
- 8 white blood cell count and differential, platelet count).
- 9 8) HBV DNA viral load, qualitative and quantitative HBeAg and HBsAg measurement
- 10 9) 50 mL of blood in heparinized green top tubes for NK and T cell analysis.
- 11 10) Blood sample for storage (5 mL of blood separated into serum and stored frozen in 0.5-1.0
- 12 mL aliquots)
- 13 11) Liver biopsy cut into four sections, one (at least 1.5 cm) placed in formalin for routine light
- 14 microscopy and the other 3 (.3cm, .5cm and 1 cm) placed in RNA later and flash frozen in
- 15 liquid nitrogen 24 hours later for RNA and protein analyses and flow cytometry. A liver
- 16 biopsy fragment of > 5 mm will be used to assess the frequency and function of NK cells.
- 17 12) Discharge from hospital

18

19

20 **Initiation of Treatment**

21

22 Patients will be stratified on the basis of HBeAg status into 2 groups of 30 patients each, to receive

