6 predictive factors associated with a favorable response to peginterferon therapy when added on to
7 long-term NUCs treatment, in patients with HBeAg positive and negative chronic HBV infection.

8

9 **Primary end-points**

10

- 11 1) The primary end-point for this study will be the change in level of ISG expression and NK cell
12 responses before and after 1st peginterferon injection in responders versus non-responders
13 to peginterferon add-on therapy.
- 14 2) Proportion of eAg positive patients showing eAg loss with or without seroconversion at end
15 of treatment and 24 and 48 weeks off therapy.
- 16 3) Proportion of eAg positive patients showing sAg loss with or without seroconversion at end
17 of treatment and 24 and 48 weeks off therapy
- 18 4) Proportion of eAg negative patients showing sAg loss with or without seroconversion at at
19 end of treatment and 24 and 48 weeks off therapy

20

21 **Secondary endpoints**

22

- 23 1. Level of qHBsAg decline at treatment week 12, at end of treatment and 24 and 48 weeks off
24 therapy, compared to pretreatment levels in eAg positive and negative patients
- 25 2. Level of qHBeAg decline at treatment week 12, at end of treatment and 24 and 48 weeks off
26 therapy, compared to pretreatment levels in eAg positive and negative patients
- 27 3. Correlation of qHBsAg levels at initial evaluation, week 12,24,36 and 48 with intrahepatic
28 pregenomic and cccDNA concentration before and after initiation of peginterferon in
29 responders versus non-responders to treatment.
- 30 4. Intrahepatic pregenomic and cccDNA concentration before and after starting treatment with
31 peginterferon.
- 32 5. Epigenetic alterations in HBeAg positive and negative patients following first 1st
33 peginterferon injection compared to pretreatment levels as measured by chromatin
34 immunoprecipitation (ChIp) assays

- 1 6. Frequency and functional activity of circulating and liver infiltrating, HBV-specific T-cells,
2 measured before and during treatment in responders versus non-responders to
3 peginterferon add-on therapy.
4

5 DOSE CHANGES 6

7 **Stopping peginterferon therapy:** 8

9 Add-on peginterferon will be discontinued early for any of the following reasons:

- 10 a) **Toxicity**- the dose of peginterferon will be modified or discontinued according to Table 1:
11 Peg-Interferon Alfa-2a Dose Modification Guidelines (see below).
12 b) **Withdrawal of informed consent** (subject's decision to withdraw for any reason.

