It is not possible to calculate power for the primary endpoints. We have calculated power for the secondary endpoints of the rates of HBeAg and HBsAg loss. Response rates in patients in both groups will be compared to historical controls of HBeAg positive and negative. It is assumed that if these patients were followed for an additional year without peginterferon, only 10% of the HBeAg positive patients would become HBeAg negative and 5% of the HBeAg negative patients would become HBsAg negative. A sample size of 29 HBeAg positive and 27 HBeAg negative patients will provide the study with a statistical power of 80% to detect a difference of 25% (35% versus 10% for HBeAg loss and 30% versus 5% for HBsAg loss). The sample size was increased to 30 patients in each arm to allow for withdrawals.

Variables to be analyzed in association with a serological response will include: baseline ALT and HBV DNA level, liver histology, HBV genotype, IL28B genotype, duration of NUC therapy, and ISG levels. Patients with missing data or who drop out of the study will be considered as treatment failures on an intention to treat basis. For comparison of means, Student's t-test will be used. All reported p-values will be 2-sided.

Demographics and Baseline Characteristics

The following will be summarized for treated subjects:

- Demographics: age, race, gender, geographic region, ethnicity;
- Disease characteristics at baseline: HBV DNA level, HBV genotype, IL28B SNP genotype and cirrhosis status, duration of NUC therapy;
- Physical measurements at baseline; height, weight, body mass index, hip and waist circumference;
- Laboratory tests at baseline;

Analysis plan

To address the primary hypothesis that ISG levels are related to virological response to peginterferon, the ISG analysis of the on treatment liver biopsy at 6 hours after the first dose of interferon will be correlated with off-peginterferon serological outcome (HBeAg loss/seroconversion and HBsAg loss). To address the hypothesis that ISG levels are related to HBsAg levels, the ISG analysis of the on treatment liver biopsy will be correlated with HBsAg levels at weeks 4, 12, 24.. The

1 analyses will be stratified by HBV genotype and duration of NUC therapy.

2

3 **Analysis methodology**

4

5 The analysis will be based on standard approaches to analysis of microarray data. Since the software
6 and approaches change frequently in this field, we will provide a broad outline of the approach

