7 rather than detailed, specific steps.

8 a) We will perform quality control and background normalization of the gene array data.

9 b) Expression value estimates will be obtained and quantile normalization and median scaling
10 of the genes will be performed.

11 c) A list of genes up- or down-regulated >2-fold with $p > 0.05$ will be prepared using the
12 following procedure:

- 13 1. For each patient, genes up- or down-regulated >2-fold in the second biopsy
14 compared to the first will be identified.
- 15 2. Lists will be prepared of genes that are up- or down-regulated >2-fold for any of the
16 subjects.
- 17 3. A paired t-test will be used to identify genes from this list that have a p value < 0.05
18 (Difference is not equal to zero).
- 19 4. The subset of the genes in (3) that are up- or down-regulated in >50% of patients in
20 groups defined relapse and/or presence of cirrhosis will be identified.
- 21 5. This procedure will be repeated with $p < 0.01$, but the primary analysis will be
22 based on the genes selected using $p < 0.05$.

23 d) The false discovery rate (FDR) of the t test will be estimated.

24 A more detailed statistical analysis plan will be developed prior to the start of data analysis.

25

26

27

HAZARDS AND DISCOMFORTS

28

The risks and discomforts of frequent phlebotomy.

30 To document stable levels of biochemical and serologic markers of chronic hepatitis and to monitor
31 the effects and toxicities of the combination of peginterferon alfa-2a and the nucleos(t)ide analogue
32 frequent blood sampling will be required. Patients will have between 11 and 12 venipunctures
33 during the study. Each venipuncture will be for approximately 20 to 75 cc of blood. The total amount
34 of blood drawn during an 8 week period will not exceed 10.5 ml/Kg or 550 mls, whichever is smaller.

35

The risks and discomforts of HIV testing.

36

1 Patients will have blood tested for anti-HIV at entry. Mention of anti-HIV is made in the consent form
2 which includes the exact language used in the standard consent form used for anti-HIV testing at the
3 Clinical Center. It is important to test for HIV infection as many of the drugs used to treat hepatitis B
4 (tenofovir, tenofovir and emtricitabine, lamivudine and entecavir) have activity against HIV and a
5 treatment regimen using only two drugs against HIV would not be considered standard of care.

7 **The risks and discomfort of percutaneous liver biopsy.**

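### Liver ISG expression is assigned to real-time PCR or nanostring but processed as gene-array data; quantile normalization on a targeted panel would bias the ISG change toward zero, by an amount that depends on an unstated panel

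*Combined protocol and SAP*

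**What the plan says.** **Endpoint.** Item 1 under Primary end-points reads: "The primary end-point for this study will be the change in level of ISG expression and NK cell" responses before and after the first peginterferon injection, compared between responders and non-responders.

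**Assay.** Under Admission for pretreatment liver biopsy, mRNA "levels of ISG's, immune cell markers and chemokines/cytokines will be quantitated by real-time" "PCR or nanostring. Intrahepatic pregenomic and cccDNA will also be quantitated by Southern" blotting or real-time PCR. The first part covers the expression targets and the last part covers viral nucleic acid. The On-treatment liver biopsy section refers back to these methods for the 6-hour sample.

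**Analysis.** Under Analysis methodology: "The analysis will be based on standard approaches to analysis of microarray data". Step a: "We will perform quality control and background normalization of the gene array data". Step b: "Expression value estimates will be obtained and quantile normalization and median scaling" of the genes. Step c then applies a per-patient filter, beginning "For each patient, genes up- or down-regulated >2-fold in the second biopsy" relative to the first, followed by a paired t-test at p < 0.05. The section calls itself a broad outline and promises a more detailed statistical analysis plan before data analysis starts.

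**Not stated anywhere.** No section assigns a microarray to the biopsies, gives the number of genes or the share that are ISGs, or names reference genes for normalization.

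**The concern.** Quantile normalization forces every sample onto one common distribution. That is sound when nearly all measured genes are stable and only a few move, as on a genome-wide array. It is not sound when a sizeable part of a small panel moves in one direction because of the treatment. The method then reads the treatment effect as a technical shift and removes part of it.

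The conditions here make that possible. The listed targets are ISGs, immune markers and chemokines/cytokines. The 6-hour time point was chosen, in the Protocol overview, because interferon-induced genes are then near their peak.

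At stake is primary end-point 1. Attenuation would shrink the before/after change and, more strongly, the difference in change between responders and non-responders. The Power calculation section says power cannot be calculated for the primary endpoints, so nothing in the plan shows that the study could absorb such a loss. A null result after two biopsies per patient could be partly an artefact of normalization.

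**Working it through.** **The plan's own figure.** There is none on this point. The only stated sample sizes (29 and 27) concern HBeAg and HBsAg loss and do not depend on it.

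**Step 1: algebra.** Let a share f of the panel be ISGs with mean true log2 change D, and let the other genes be unchanged on average. Quantile normalization gives every sample the same mean, so the average change over all genes after normalization must be 0. A uniform shift c that achieves this satisfies f·D − c = 0, so c = f·D. The ISG change that remains is D − f·D = (1 − f)·D, and the unchanged genes appear to fall by f·D. The retained share of the mean ISG change is therefore at most about 1 − f: 90% at f = 0.10, 75% at 0.25, 50% at 0.50 and 20% at 0.80. If some of the non-ISG targets are also induced, the effective f is larger.

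**Step 2: why the contrast suffers more than the mean.** Quantile normalization also caps the upper tail, so larger inductions are compressed more. Take an illustration with assumed 8-fold and 4-fold induction, 200 genes, 25% ISGs, gene SD 2 and noise SD 0.3:
- Responders: true 3.01, after normalization 1.97, so 1.97/3.01 = 65% retained.
- Non-responders: true 2.01, after normalization 1.45, so 1.45/2.01 = 72% retained.
- Contrast: true 3.01 − 2.01 = 1.00, after normalization 1.97 − 1.45 = 0.52, so 52% retained.

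**Step 3: size over a range of panels.** The inputs are assumptions, not taken from the documents: induction 4-fold in responders and 2-fold in non-responders (true contrast log2 4 − log2 2 = 1.0), log2 noise SD 0.4, and SD of expression between genes 1 to 3. The split is 19 responders and 41 non-responders. It is consistent with the plan's target rates: 0.35 × 30 + 0.30 × 30 = 19.5 of 60.

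| Panel | ISG share | Bound 1 − f | Contrast retained |
|---|---|---|---|
| 40 genes | 25% | 75% | 46-59% |
| 40-100 genes | 50% | 50% | 29-43% |
| 100 genes | 80% | 20% | 13-18% |
| 800 genes | 10% | 90% | 67-86% |
| 20,000 genes (array) | 1.5% | 98.5% | 89-99% |

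A second set of assumptions (8-fold versus 4-fold, noise SD 0.3, gene SD 1 to 3) gives the same direction and wider ranges: 67-97% retained at 1% ISGs, 34-80% at 10%, 24-61% at 25%, 15-38% at 50% and 8-20% at 75%.

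**Step 4: effect on step c.** With true 4-fold induction, gene SD 2 and noise SD 0.3, the share of ISGs whose mean change passes the 2-fold filter falls from about 0.97 array-wide to 0.43 when ISGs are half the panel. In that case unchanged genes appear down by 0.89 log2, so the gene list could lose real ISGs and gain false down-regulation.

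**Step 5: median scaling.** After quantile normalization all samples already share one median, so scaling by sample does nothing further. Scaling by gene removes the same constant from both biopsies on the log scale and leaves paired differences unchanged. It is not a separate source of bias.

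**Step 6: the alternative.** Normalizing each sample to 10 stable reference genes, under the 8-fold versus 4-fold assumptions, returns changes of about 3.0 and 2.0 at every ISG share. The full contrast of 1.0 is kept.

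**The case against.** The best counter-argument is that a genome-wide array may have been intended. The statistical section does name microarray and gene-array data, and step b follows from step a. The Hypothesis section speaks of a transcription profile, and biopsy tissue is preserved for RNA analysis in general. On that reading PCR or nanostring is a separate targeted measurement and step b is orthodox, with 89-99% of the contrast retained under the assumptions above. The text is also only an outline, and platform-specific normalization is the kind of detail the promised analysis plan would hold.

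Much of this stands. The documents leave room for an array, and the outline status lowers the urgency. But no section assigns an array to the biopsies, while one section expressly assigns ISG mRNA to PCR or nanostring. One of the two texts must change whichever platform is used. Step b is also written out explicitly, so the later plan would either inherit it or contradict it.

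A reader might infer more: that the plan as written would erase most of the ISG induction. The documents do not support that. They give no panel size and no ISG share, and the target list includes immune markers and cytokines as well as ISGs. Losing most of the mean induction requires ISGs to be about half or more of the panel.

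**Conclusion.** The mismatch between assay and analysis is a matter of text and needs no assumption. If step b is applied to a targeted PCR or nanostring panel, the ISG change and the responder contrast are biased toward zero, provided the remaining genes are stable or also rise.

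The size is conditional on panel composition, fold induction and expression spread, none of which the documents state. It runs from slight on a genome-wide array to a loss of more than half of the contrast once ISGs make up half of a 40-100 gene panel (100 − 43 = 57% to 100 − 29 = 71% lost). These figures show the possible scale; they do not forecast this trial's result. The bias comes from quantile normalization alone. The point should be corrected, but because the text is an outline it is not a fatal flaw in the design.

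**What to change.** 1. Reconcile the Admission for pretreatment liver biopsy section with the Analysis methodology section: state which platform supplies the data for primary end-point 1, and give the gene panel.
2. Rewrite step b by platform. For PCR or nanostring, normalize each sample to pre-specified reference genes, add the spike-in controls for nanostring, and apply no quantile normalization across the panel. Keep quantile normalization only if a whole-genome array is actually used.
3. Put this in the protocol or the promised statistical analysis plan before serological outcomes are known, so that the choice cannot be influenced by the results.

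The cost is about one paragraph of wording and the selection of reference genes, which these assays need in any case. No sample size, visit or procedure changes.

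### The gene-selection steps never use responder status, so genes that change mainly in responders can be lost before primary end-point 1 is analysed

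*Combined protocol and SAP*

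**What the plan says.** Under Primary end-points, item 1 is the change in ISG expression and NK cell "responses before and after 1st peginterferon injection in responders versus non-responders" to add-on therapy.

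The only stepwise gene analysis is in STATISTICAL ANALYSIS, Analysis methodology, step c. I call its numbered items c1 to c5.

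- **c1 and c2:** fold change between the two biopsies is computed per patient. "Lists will be prepared of genes that are up- or down-regulated >2-fold for any of the" subjects. One patient is enough for a gene to enter.
- **c3:** "A paired t-test will be used to identify genes from this list that have a p value < 0.05". The null is zero mean change. The patients included are not stated, and no split by response is named.
- **c4:** "The subset of the genes in (3) that are up- or down-regulated in >50% of patients in" "groups defined relapse and/or presence of cirrhosis will be identified".
- **c5:** the procedure is repeated at p below 0.01, but the primary analysis rests on the genes chosen at p below 0.05.

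Step d estimates the false discovery rate of the t-test. Clinical Definitions covers HBeAg loss, HBsAg loss and sustained response, but not relapse. Separately, the Analysis plan says that the ISG result from the biopsy 6 hours after the first dose of "interferon will be correlated with off-peginterferon serological outcome (HBeAg loss/seroconversion and HBsAg loss"). A fuller SAP is promised before data analysis starts.

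**The concern.** The end-point is a between-group contrast of change, whereas the selection rule looks at overall change (c3) and at how common a change is in groups formed on other characteristics (c4). A gene can separate responders from non-responders perfectly and still be changed in only a minority of all patients, or of cirrhotic or non-cirrhotic patients. A majority rule applied in those groups works against such a gene, and a responder test run afterwards on the surviving list could not recover it.

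The comparison is the main reason that patients have a second biopsy. If the c4 subset feeds the primary analysis, a finding of no ISG difference could reflect the selection rule rather than biology. c5 leaves open which list is used, so that choice could also be made after the data are seen.

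**Working it through.** **Inputs from the plan.** 30 patients per HBeAg group, and the power calculation's target to "detect a difference of 25% (35% versus 10% for HBeAg loss and 30% versus 5% for HBsAg loss"). Expected responders: 0.35 × 30 + 0.30 × 30 = 10.5 + 9 = 19.5, so about 20 of 60 (32.5% before rounding).

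**The plan's own figure.** None is given for the gene filter. The sample sizes that accompany these rates do reproduce with n = p1(1 − p1)(1.96 + 0.84)² / (p1 − p0)², using unrounded normal quantiles and an assumed two-sided alpha of 0.05. For 35% versus 10% it gives 28.57, hence 29. For 30% versus 5% it gives 26.37, hence 27. They are not in dispute; only the response rates matter here.

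**Assumptions not in the documents.** The gene shifts by 1.0, 1.5 or 2.0 log2 units in responders and by 0 in the others. The SD of paired change is 0.5, 0.7 or 1.0. Each patient has a 20% chance of cirrhosis, independent of response. c3 pools all patients. Changed means more than 2-fold in either direction.

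**c3 alone.** With one third responding, the pooled mean is δ/3 and the pooled SD is √(σ² + δ² × 1/3 × 2/3). For δ = 1 and σ = 0.7 these are 0.333 and √(0.49 + 0.222) = 0.844, so the expected t is 0.333 × √60 / 0.844 = 3.06. For σ = 1.0 the SD is 1.106 and the expected t is 2.33. c3 therefore usually retains the gene.

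**c4 for a perfect, noise-free gene.** Over all patients it is changed in 20/60 = 33%, below the 50% cut. In a group unrelated to response, more than half must be responders. At 32.5% that has binomial probability 5.9% for 12 patients (20% of 60) and 0.4% for 48.

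**c3 and c4 together.** Simulation of 20 responders and 40 non-responders, 20,000 runs per row:

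| log2 shift | SD | Passes c3 | c3, and c4 in either cirrhosis group | c3, and c4 over all patients pooled | c3, and c4 in responder groups |
|---|---|---|---|---|---|
| 1.0 | 0.5 | 99.2% | 0.6% | 0.0% | 41.1% |
| 1.0 | 0.7 | 89.6% | 3.1% | 0.0% | 39.9% |
| 1.0 | 1.0 | 64.3% | 13.7% | 1.6% | 36.6% |
| 1.5 | 0.5 | 100% | 5.6% | 0.0% | 100% |
| 1.5 | 0.7 | 99.6% | 12.0% | 0.1% | 98.7% |
| 1.5 | 1.0 | 91.8% | 39.7% | 13.3% | 88.1% |
| 2.0 | 0.5 | 100% | 10.3% | 0.0% | 100% |
| 2.0 | 0.7 | 100% | 23.9% | 1.3% | 100% |
| 2.0 | 1.0 | 99.0% | 67.4% | 38.2% | 98.9% |

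The higher c4 rates at SD 1.0 arise because noise carries many non-responders past 2-fold, not because the rule detects response. At SD 0.5 to 0.7, a direct two-sample test of 20 against 40 (one gene, unadjusted 5% level) detects every one of these genes in 99.9 to 100% of runs.

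**Where c3 does lose genes.**

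- **Few responders:** at a 10% response rate it passes 10 to 49% of these genes with 60 patients.
- **Small shift:** at +0.8 SD in responders only, it passes 48%, against 82% unadjusted power for the direct test.
- **Opposite directions:** at +0.8 SD in responders and −0.4 SD in non-responders, the pooled mean is (20 × 0.8 − 40 × 0.4)/60 = 0. c3 passes 2.5%, and the direct test has 99% power.

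**The case against.** A reader might infer that responder-only genes are always discarded before any responder comparison. The documents do not support that.

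- **Nothing is explicitly dropped.** c4 identifies a subset; it does not say that the other genes are removed. The p-value criterion named in c5 is the one in c3, so the c3 list may be what is meant.
- **A comparison outside the filter is planned.** The Analysis plan's correlation of ISG results with serological outcome is not tied to the filtered list. ISG mRNA is also to be measured by real-time PCR or nanostring, to which a microarray filter need not apply. The NK cell half of the end-point is unaffected.
- **Relapse might mean treatment failure.** c4 would then work within response groups and keep 88 to 100% of genes with a log2 shift of 1.5 to 2.0.
- **c3 is not the main fault.** Its worst figures need a small shift (0.8 SD is 0.4 to 0.8 log2 units at SD 0.5 to 1.0, below 2-fold) or movement in opposite directions, for which the documents give no support.
- **The section calls itself a broad outline,** and a fuller SAP is to follow.

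These points stand as limits on the claim. They do not remove it. Relapse ordinarily presupposes a prior response, so relapse groups are not plainly responder groups, and the plan does not define them. The planned correlation names no test, does not say which genes enter, and refers to the 6-hour biopsy rather than to the change between biopsies. A later SAP does not by itself correct a grouping that is already written down.

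**Conclusion.** The concern holds in a conditional form. On every reading, the selection steps do not use response, and none of them tests the contrast in primary end-point 1. Whether responder-specific genes are actually lost depends on two matters that the plan leaves open: which list feeds the primary analysis, and what the c4 groups are.

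If the c4 subset is used with groups unrelated to response, the loss is large at moderate noise: roughly three quarters or more of responder-only genes at SD 0.5 to 0.7, and nearly all if patients are pooled. At SD 1.0 the loss is smaller but still substantial. If the c3 list is used, or the c4 groups are responders and non-responders, most genes with a clear shift survive. These sizes rest on my assumed shifts, SDs and cirrhosis share, and on c3 pooling all patients, which is inferred. The stronger conclusion, that the trial will miss its ISG difference because of the filter, does not follow from the text.

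**What to change.** For primary end-point 1, state in the SAP that the responder versus non-responder difference in within-patient log2 change (second biopsy minus first) will be tested directly. Do this for every gene that passes quality control, or for a prespecified ISG set, and control the false discovery rate on that test. Name the serological outcome and time point that define a responder.

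Keep c3 as a description of what peginterferon induces overall. In c4, replace the relapse and cirrhosis groups with responders and non-responders, or drop c4 as a filter for this end-point. Say in c5 which list any remaining analysis uses. In the same edit, reconcile the opening line of step c, which gives p above 0.05, with c3 and c5, which give p below 0.05.

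The cost is SAP wording and one more test per gene, with no new data or samples. The drawback is a longer list for the multiplicity adjustment, so power per gene will be below the unadjusted figures above. A prespecified ISG set would limit that.

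### The numbered ISG procedure looks at patient groups only through a 2-fold, >50% count, and no stated step compares the size of the ISG change between responders and non-responders

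*Combined protocol and SAP*

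**What the plan says.** All places are in the combined protocol and SAP.

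- **Primary end-points, item 1:** "The primary end-point for this study will be the change in level of ISG expression and NK cell" "responses before and after 1st peginterferon injection in responders versus non-responders". This is a measured change per patient, contrasted between outcome groups.
- **Analysis methodology, c1:** "For each patient, genes up- or down-regulated >2-fold in the second biopsy" compared with the first are identified, which gives a yes/no per patient and gene.
- **c2:** "Lists will be prepared of genes that are up- or down-regulated >2-fold for any of the" subjects, so one patient past the cut admits a gene.
- **c3:** "A paired t-test will be used to identify genes from this list that have a p value < 0.05". This uses the full scale, before versus after, with no group term.
- **c4:** "The subset of the genes in (3) that are up- or down-regulated in >50% of patients in" "groups defined relapse and/or presence of cirrhosis will be identified". No test, estimate or interval is attached. The 2-fold meaning of regulated is carried over from c1 and c2, not restated.
- **c5 and (d):** the primary analysis rests on the genes selected at p < 0.05, and a false discovery rate is estimated for the t-test.
- **Analysis plan:** separately, the ISG analysis of the biopsy taken 6 hours after the first dose of "interferon will be correlated with off-peginterferon serological outcome". Neither the measure (6-hour level or paired change), its scale nor a test is given.
- **Power calculation:** ISG levels are listed among variables to be related to serological response. Student's t-test is named for comparing means in general. Power for the primary endpoints is said not to be calculable.

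**The concern.** Every participant has two liver biopsies so that the intrahepatic interferon response can be measured as a change. The question is whether the strength of that response differs by outcome. In the numbered procedure, strength is discarded before groups are considered: each patient's change is cut at 2-fold, and the group is then cut at 50%.

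For a gene induced well above 2-fold, nearly everyone is a yes in both groups, and a real difference in strength leaves no trace. For a gene averaging about 2-fold, sampling noise can put one group above 50% and the other below when nothing differs, with no error rate to warn the reader. The documents give no reason for the 2-fold cut.

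Neither c3, which has no group term, nor the Analysis plan correlation, which has no stated measure or test, fills the gap.

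**Working it through.** **1. The plan's own figure.** The only stated sample-size figures concern serological loss: 29 patients (35% versus 10%) and 27 (30% versus 5%) for 80% power. They reproduce with n = (1.960 + 0.842)² × p₁(1 − p₁)/(p₁ − p₀)², taking two-sided 0.05:
- 7.849 × 0.35 × 0.65/0.25² = 28.6, so 29
- 7.849 × 0.30 × 0.70/0.25² = 26.4, so 27

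There is no corresponding figure for the ISG end-point, so the rest is illustration.

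**2. Inputs.**
- Group sizes: 0.35 × 30 + 0.30 × 30 = 10.5 + 9 = 19.5, taken as 19 responders and 41 non-responders of 60.
- log2 fold change is assumed normal with a common SD of 0.5 to 1.0. The documents give no ISG SD.
- The true difference is assumed to be 0.79 SD, with responders higher. It is chosen so that the full-scale test has about 80% power.
- Alpha is two-sided 0.05 per gene, unadjusted.

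**3. Full scale.** The noncentrality is 0.79 × √(19 × 41/60) = 0.79 × 3.603 = 2.85, with 58 degrees of freedom and critical t 2.002. Power is 79.9%. For the same difference it is about 58% at alpha 0.01 and 28% at 0.001.

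**4. The c4 flag.** With mean μ and SD σ in log2 units, the chance that a patient passes the cut is p = Φ((μ − 1)/σ) + Φ((−1 − μ)/σ). A group is flagged if more than half pass: at least 10 of 19, or at least 21 of 41 (binomial). The responder flag comparison shown is what c4 would do if applied to those groups.

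| Mid-point of the two group means | True difference | SD | Share past cut, responders vs non-responders | Flagged in both | Flagged in one only |
|---|---|---|---|---|---|
| 8-fold | 0.79 SD | 0.5–1.0 | 99–100% vs 95–100% | about 100% | about 0% |
| 4-fold | 0.79 SD | 0.5 | 99% vs 95% | at least 99.9% | under 0.1% |
| 4-fold | 0.79 SD | 1.0 | 92% vs 73% | 99.9% | 0.1% |
| 2-fold | 0.79 SD | 0.5–1.0 | 65–66% vs 35–40% | 2–9% | 85–90% |
| 2-fold | none | 0.5–1.0 | 50–52% in each | – | 48–50% |
| 1.4-fold | 0.79 SD | 0.5 | 27% vs 9% | about 0% | 2% |
| 1.4-fold | 0.79 SD | 1.0 | 49% vs 32% | 0.4% | 46% |

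**5. Do weakly induced genes leave the list altogether?** Take 1.8-fold (log2 0.848) and SD 0.5. A patient passes the cut with probability 0.38. The chance that none of 60 does is 0.62⁶⁰, far below 0.001, so c2 admits the gene. In c3 the expected t is about 0.848/(0.5/√60) = 13, so it is kept there too. It can be lost only at c4.

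**The case against.** Step c produces a gene list. c3 selects on the full scale, c5 can be read as resting the primary analysis on the c3 selection, and c4 only marks a subset. The primary hypothesis is addressed elsewhere, by the Analysis plan correlation, where no 2-fold cut appears. c4's groups are relapse and/or cirrhosis, so responder figures model a comparison it does not make. The methodology also describes itself as a broad outline, with a detailed SAP to follow.

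Much of this stands, and it rules out three stronger readings that a reader might infer:

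- **That c4 is the plan's only group-level ISG analysis.** It is the only one in the numbered procedure. The Analysis plan correlation is another, though unspecified.
- **That weakly induced genes cannot show a difference or are dropped.** They still enter through c2 and c3. Whether c4 hides them depends on an SD the documents do not give: one-group-only listing at 1.4-fold runs from 2% to 46%.
- **That the plan loses a stated amount of power.** c4 has no test, so it has no power to lose. The 80% is a per-gene benchmark under assumed inputs, not a protocol figure.

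The objection does not supply the missing analysis. The correlation could be run on the 6-hour level alone, on any scale. Replacing c4's groups with responders and non-responders would leave the double cut in place. The deferred SAP is where the correction belongs; it does not show that one has been made.

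**Conclusion.** The point holds in this form. Within the numbered procedure, groups are compared only by an untested count of patients past 2-fold. Across the whole document, no stated step compares the size of the paired ISG change between responders and non-responders, as primary end-point 1 requires.

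The blindness is firm for strongly induced genes: over the assumed SD range of 0.5 to 1.0, a gene averaging 4-fold or more is listed for both groups at least 99.9% of the time despite a 0.79 SD difference. Near 2-fold the flags do separate under that difference (85–90%), but they also separate 48–50% of the time with no difference, so a one-group listing is not evidence by itself. For weaker genes no general statement is possible without the SD.

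The sizes rest on normal log2 fold changes, a 19/41 split and an unadjusted 0.05. The structural conclusion does not depend on them. This should be corrected before analysis; it does not invalidate the design.

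**What to change.** In c4, and as the definition of the Analysis plan correlation, take each patient's log2 fold change (second minus first biopsy) as the outcome. Compare it between responders and non-responders with a per-gene linear model. Report each estimated difference with its confidence interval, and extend the false discovery rate in (d) to this comparison. Keep the 2-fold and >50% counts as descriptive columns, not as conditions for a gene to enter or leave the list.

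The cost is wording in Analysis methodology, the Analysis plan and the promised detailed SAP; samples and assays are unchanged. There are two downsides. Some listed genes will have mean changes below 2-fold, which the descriptive column will show. Per-gene power will fall once multiplicity is controlled: for the difference used above, from about 80% to about 58% at alpha 0.01.
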